9.6.1.2 Overall Survival

The nonparametric Kaplan-Meier method will be used to estimate the survival curves. The treatment difference in survival will be assessed by the stratified log-rank test (based on the stratification factors defined in Section 6.3.2). A stratified Cox proportional hazard model with Efron's method of tie handling will be used to assess the magnitude of the treatment difference (ie, the HR). The HR and its 95% CI from the stratified Cox model with a single treatment covariate will be reported.

A horizontal bar of blacked-out text is positioned below the main text block, spanning approximately two-thirds of the page width.

9.6.1.3 Progression-free Survival at 2 Years

Progression-free survival at 2 years and 95% CI will be estimated using Kaplan-Meier method. The approach for testing on difference in outcome at a fixed point in time will be used for comparison of the PFS rate at 2 years between 2 treatment groups [Klein, J. P. 2003]. The difference in PFS rate at 2 years, its 95% confidence interval and nominal p-value will be reported.

9.6.1.4 Overall Survival at 3 Years

Overall survival at 3 years and 95% CI will be estimated using Kaplan-Meier method. The approach for testing on difference in outcome at a fixed point in time will be used for comparison of the OS rate at 3 years between 2 treatment groups [Klein, J. P. 2003]. The difference in OS rate at 3 years, its 95% confidence interval and nominal p-value will be reported.

[figure not shown]
[figure not shown]
9.6.1.5 Objective Response Rate

Stratified Miettinen and Nurminen's method will be used for comparison of the objective response rate (ORR) between 2 treatment groups [Miettinen, O. and Nurminen, M. 1985].

The difference in ORR and its 95% confidence interval from the stratified Miettinen and Nurminen's method with strata weighting by sample size will be reported. The stratification factors used for randomization (See Section 6.3.2) will be applied to the analysis.

9.6.1.6 Duration of Response

For participants with measurable at baseline who demonstrate CR or PR, DOR is defined as the time from first documented evidence of CR or PR until disease progression or death due to any cause, whichever occurs first. Censoring rules for DOR are summarized in [Table 8](#). DOR will be assessed using RECIST 1.1 by investigator and BICR, respectively. For each DOR analysis, a corresponding summary of the censoring reasons for responding participant will also be provided.

A summary of the primary analysis strategy for the key efficacy endpoints is provided in [Table 9](#).

Table 9 Efficacy Analysis Methods for Key Efficacy Endpoints

| Endpoint/ Variable | Statistical Method | Analysis Population | Missing Data Approach |
|--|--|------------------------|--|
| Primary Analyses: | | | |
| PFS per RECIST 1.1 by investigator or by histopathologic confirmation | Testing: Stratified log-rank test Estimation: Stratified Cox model with Efron's tie handling method | ITT | Censored according to rules in Table 7 |
| OS | Testing: Stratified log-rank test Estimation: Stratified Cox model with Efron's tie handling method | ITT | Censored at last known alive date |
| Secondary Analyses: | | | |
| PFS per RECIST 1.1 by BICR | Testing: Stratified log-rank test Estimation: Stratified Cox model with Efron's tie handling method | ITT | Censored according to rules in Table 7 |
| Abbreviations: BICR=blinded independent central review; ITT=intention-to-treat; OS=overall survival; PFS=progression-free survival; RECIST 1.1=Response Evaluation Criteria in Solid Tumors version 1.1. | | | |

9.6.2 Statistical Methods for Safety Analyses

Safety and tolerability will be assessed by clinical review of all relevant parameters including AEs, laboratory tests, vital signs, and ECG measurements.

The analysis of safety results will follow a tiered approach ([Table 10](#)). The tiers differ with respect to the analyses that will be performed. Adverse events (specific terms as well as system organ class terms) and events that meet predefined limits of change in laboratory values, vital signs, and ECG parameters are either prespecified as “Tier 1” endpoints or will be classified as belonging to “Tier 2” or “Tier 3” based on the observed proportions of participants with an event.

Tier 1 Events

Safety parameters that are identified a priori constitute “Tier 1” safety endpoints that will be subject to inferential testing for statistical significance. Adverse events of special interest that are immune-mediated or potentially immune-mediated are well documented and will be evaluated separately; however, these events have been characterized consistently throughout the pembrolizumab clinical development program and determination of statistical significance is not expected to add value to the safety evaluation. Additionally, there are no known AEs associated with participants with treatment for which determination of a p-value is expected to impact the safety assessment. Therefore, there are no Tier 1 events in this study.

Tier 2 Events

Tier 2 parameters will be assessed via point estimates with 95% CIs provided for differences in the proportion of participants with events (via the Miettinen and Nurminen method) [Miettinen, O. and Nurminen, M. 1985].

Membership in Tier 2 requires that at least 5% participants in any treatment group exhibit the event; all other AEs and predefined limits of change will belong to Tier 3. The threshold of at least 5% participants was chosen for Tier 2 events because the population enrolled in this study is in critical condition and usually experiences various AEs of similar types regardless of treatment; events reported less frequently than 5% participants would obscure the assessment of the overall safety profile and add little to the interpretation of potentially meaningful treatment differences. In addition, Grade 3 to 5 AEs ($\geq 5\%$ participants in 1 of the treatment groups) and SAEs ($\geq 2\%$ participants in 1 of the treatment groups) will be considered Tier 2 endpoints. Because many 95% CIs may be provided without adjustment for multiplicity, the CIs should be regarded as a helpful descriptive measure to be used in safety review, not as a formal method for assessing the statistical significance of the between-group differences.

Tier 3 Events

Safety endpoints that are not Tier 1 or 2 events are considered Tier 3 events. The broad AE categories consisting of the proportion of participants with any AE, a drug-related AE, a serious AE, an AE which is both drug-related and serious, a Grade 3-5 AE, a drug-related Grade 3-5 AE, and discontinuation due to an AE will be considered Tier 3 endpoints. Only point estimates by treatment group are provided for Tier 3 safety parameters.

Continuous Safety Measures

For continuous measures such as changes from baseline in laboratory, vital signs, and ECG parameters, summary statistics for baseline, on-treatment, and change from baseline values will be provided by treatment group in table format.

Table 10 Analysis Strategy for Safety Parameters

| Safety Tier | Safety Endpoint | p-Value | 95% CI for Treatment Comparison | Descriptive Statistics |
|--|---|---------|---------------------------------|------------------------|
| Tier 2 | Grade 3 to 5 AE (incidence $\geq 5\%$ of participants in one of the treatment groups) | | X | X |
| | Serious AE (incidence $\geq 5\%$ of participants in one of the treatment groups) | | X | X |
| | AEs (incidence $\geq 5\%$ of participants in one of the treatment groups) | | X | X |
| Tier 3 | Any AE | | | X |
| | Any Grade 3 to 5 AE | | | X |
| | Any Serious AE | | | X |
| | Any Drug-related AE | | | X |
| | Any Serious and Drug-related AE | | | X |
| | Any Grade 3 to 5 and Drug-related AE | | | X |
| | Discontinuation due to AE | | | X |
| | Death | | | X |
| | Specific AEs, SOCs (incidence $< 5\%$ of participants in all of the treatment groups) | | | X |
| Abbreviations: AE = adverse event; CI = confidence interval; SOC = system organ class. | | | | |

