6.4.1 Pembrolizumab or Placebo

The first infusion of pembrolizumab or placebo combined with chemoradiotherapy may begin up to 3 days after randomization.

The standard dosing window for pembrolizumab or placebo is 21 days (\pm 3 days) during Q3W dosing and 42 days (\pm 3 days) during Q6W dosing.

Interruptions from the protocol-specified treatment plan for more than 3 weeks between pembrolizumab doses for nondrug-related or administrative reasons require consultation between the investigator and the Sponsor and written documentation of the collaborative decision on participant management.

Participants must receive 5 infusions of pembrolizumab or placebo Q3W before moving to Q6W dosing. The interval between Cycle 5 and Cycle 6 is 3 weeks \pm 3 days. Q6W dosing starts from Cycle 6 onwards. Chemoradiotherapy and brachytherapy are administered during the Q3W dosing regimen. Pembrolizumab or placebo infusions should be continued during cisplatin or radiotherapy delay. Note: On treatment days where both pembrolizumab/placebo and cisplatin are administered, it is preferable for pembrolizumab/placebo to be administered prior to cisplatin. However, cisplatin may be administered prior to pembrolizumab/placebo per local standard practice.

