6.4.2.2 External Beam Radiotherapy

Pelvic EBRT is an integral part of the overall treatment strategy with the primary aim of obtaining regional and nodal control.

It is currently delivered with different techniques: 3D conformal EBRT, IMRT, or VMAT over 40 days. Daily image guidance is mandatory with couch correction according to bony structures if IMRT or VMAT is used. The definition of primary tumor targets is CT- and MRI-based. An individualized ITV-T is recommended based on participant anatomy and target motion. Nodal target (CTV-E) is defined according to risk of nodal spread and involved nodes or parametria are boosted, when possible, using SIB to reach a minimum radiation dosing of 80 Gy for volume-directed and 75 Gy for point-directed [Landberg, T., et al 1993] [Landberg, T., et al 1999]. Refer to the Radiation Manual for further guidance.

The main advantage of IMRT is the ability to deliver a high dose of radiation to tumor tissue while restricting dose exposure of adjacent noncancerous tissues. The overall volume irradiated to 43 Gy during EBRT is known to be associated with acute and late morbidity [Stanic, S. 2013] [Sondergaard, J., et al 2014] [Letschert, J. G. J., et al 1994]. By reducing the volume of normal tissues irradiated, IMRT reduces the risk of acute [Naik, A., et al 2016] [Gandhi, A. K., et al 2013] and late [Mundt, A. J., et al 2002] [Chopra, S., et al 2015] morbidity [Koop, A. H., et al 2016], including urinary and bowel morbidity. Furthermore, image guided radiotherapy allows tight treatment margins to be applied which has significant potential to reduce the overall volume irradiated with EBRT.

VMAT is a complex IMRT technique. In the process of irradiation, it can adjust the beam intensity from different beam directions by way of altering the dose rate and gantry rotation speed. VMAT allows to reduce treatment time, thus improving performance. It integrates the advantages of speed and dose distribution of rotational therapy and dynamic IMRT [Holt, A., et al 2011]. According to a recently reported study, VMAT plans showed superior dose coverage of the PTV, better protection of the rectum and bladder in dosimetry, and significantly reduced monitor units and treatment time compared with f-IMRT. Clinical results were similar for both plans[Guo, M., et al 2018].

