| Diarrhea/Colitis | Grade 2 or 3 | Withhold | 
 Administer corticosteroids (initial dose of 1 to 2 mg/kg prednisone or equivalent) followed by taper | 
 Monitor participants for signs and symptoms of enterocolitis (ie, diarrhea, abdominal pain, blood or mucus in stool with or without fever) and of bowel perforation (ie, peritoneal signs and ileus) Participants with \geqGrade 2 diarrhea suspecting colitis should consider GI consultation and performing endoscopy to rule out colitis Participants with diarrhea/colitis should be advised to drink liberal quantities of clear fluids. If sufficient oral fluid intake is not feasible, fluid and electrolytes should be substituted via IV infusion |
| | Recurrent Grade 3 or Grade 4 | Permanently discontinue | | |

| irAEs | Toxicity Grade (CTCAE v5.0) | Action With Pembrolizumab Monotherapy, Coformulations or IO Combinations | Corticosteroid and/or Other Therapies | Monitoring and Follow-up |
|---|--|--|--|---|
| AST or ALT Elevation or Increased Bilirubin | Grade 2 ^a | Withhold | 
 Administer corticosteroids (initial dose of 0.5 to 1 mg/kg prednisone or equivalent) followed by taper | 
 Monitor with liver function tests (consider weekly or more frequently until liver enzyme value returned to baseline or is stable) |
| | Grade 3 ^b or 4 ^c | Permanently discontinue | 
 Administer corticosteroids (initial dose of 1 to 2 mg/kg prednisone or equivalent) followed by taper | |
| T1DM or Hyperglycemia | New onset T1DM or Grade 3 or 4 hyperglycemia associated with evidence of β -cell failure | Withhold ^d | 
 Initiate insulin replacement therapy for participants with T1DM Administer antihyperglycemic in participants with hyperglycemia | 
 Monitor participants for hyperglycemia or other signs and symptoms of diabetes |
| Hypophysitis | Grade 2 | Withhold | 
 Administer corticosteroids and initiate hormonal replacements as clinically indicated | 
 Monitor for signs and symptoms of hypophysitis (including hypopituitarism and adrenal insufficiency) |
| | Grade 3 or 4 | Withhold or permanently discontinue ^d | | |

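### Adverse events are compared between arms with no split by treatment phase, which dilutes a post-chemoradiotherapy excess in events that chemoradiotherapy also causes

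*Combined protocol and SAP*

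**What the plan says.** Section 9.6.2 defines no Tier 1 events. For Tier 2, "Tier 2 parameters will be assessed via point estimates with 95% CIs provided for differences in the proportion of participants with events", using the Miettinen-Nurminen method. Table 10 applies this to all AEs, Grade 3 to 5 AEs and serious AEs that reach an incidence threshold. For the rest, "Only point estimates by treatment group are provided for Tier 3 safety parameters". Section 9.6.2 justifies the threshold by saying that this population "usually experiences various AEs of similar types regardless of treatment". AEs of special interest that are "immune-mediated or potentially immune-mediated are well documented and will be evaluated separately"; the list, the method and the period are not given.

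Nothing in 9.6.2, 9.11 or 9.12 divides AEs by treatment phase or plans time to onset, recurrent events or exposure-adjusted rates. Section 9.12 summarizes exposure in cycles only. Section 9.6.2 names no analysis window. Section 8.4.1 collects AEs from randomization to 30 days after study intervention stops, and SAEs to 90 days (30 if new anticancer therapy starts).

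On timing, Section 6.4.1 says "Chemoradiotherapy and brachytherapy are administered during the Q3W dosing regimen". Section 6.4.2 gives chemoradiotherapy 50 days, with 56 as the maximum for unforeseen delays.

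**The concern.** Some harms listed as immune-related in Table 4 share AE terms with toxicity of the background treatment, which both arms receive:

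- **Bowel.** Table 4 lists diarrhea/colitis, with the instruction "Monitor participants for signs and symptoms of enterocolitis". Section 6.4.2.2 describes morbidity of external beam radiotherapy, "including urinary and bowel morbidity".
- **Renal.** Table 4 grades nephritis by raised creatinine or acute kidney injury. Section 6.6.3 covers renal effects of cisplatin.
- **Neurological.** Table 4 lists neurological toxicities, and Section 6.6.3 covers those of cisplatin.

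If each participant counts once per term, someone with radiation diarrhea in the second month is already a case. Immune-related diarrhea a year later then adds nothing to the table. Most of the planned pembrolizumab exposure comes after chemoradiotherapy, so for shared terms the plan's only between-arm AE intervals would understate added late toxicity in a population treated with curative intent.

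**Working it through.** **Timeline.** Section 9.6.2 gives no expected AE rate or precision, so there is no plan figure to reproduce; the schedule comes first. Cycles 1 to 5 start at weeks 0, 3, 6, 9 and 12. Cycle 6 follows 3 weeks after Cycle 5, at week 15. The other 14 Q6W infusions put Cycle 20 at week 15 + 14 × 6 = 99. The AE window for someone who completes treatment is 99 + 30/7 ≈ 103 weeks. Chemoradiotherapy takes 50 to 56 days (7.1 to 8.0 weeks), or 7% to 8% of that window. It therefore ends about 7 to 8 weeks before Cycle 6.

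**Model.** Inputs: n = 490 per arm (Section 9.1). The following are assumptions: background incidence b during chemoradiotherapy, equal in both arms; later incidence 10% with pembrolizumab and 5% with placebo; later events independent of earlier ones; no pembrolizumab excess during chemoradiotherapy; everyone observed in both periods.

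Proportion ever affected, per arm: E = b + (1 − b)p. Difference between arms: (1 − b)(0.10 − 0.05). SE = √[(E₁(1 − E₁) + E₀(1 − E₀))/490], a normal approximation to the planned interval. The chance that the 95% CI excludes zero is about Φ(z − 1.96).

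| Comparison | Pembrolizumab v placebo | Difference (points) | 95% CI half-width | z | Chance CI excludes 0 |
|---|---|---|---|---|---|
| Late events only | 10.0% v 5.0% | 5.0 | 3.3 | 2.98 | 85% |
| Whole window, b = 5% | 14.5% v 9.75% | 4.75 | 4.1 | 2.28 | 63% |
| b = 10% | 19.0% v 14.5% | 4.5 | 4.7 | 1.89 | 47% |
| b = 20% | 28.0% v 24.0% | 4.0 | 5.5 | 1.43 | 30% |
| b = 30% | 37.0% v 33.5% | 3.5 | 6.0 | 1.15 | 21% |
| b = 50% | 55.0% v 52.5% | 2.5 | 6.2 | 0.79 | 12% |

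Two things happen: the difference shrinks by (1 − b), and up to b = 50% the interval widens because the proportions move towards one half.

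**Sensitivity.**
- *Other late rates.* With 9% v 3%, the late-only interval excludes zero with probability 98%, and the whole-window interval at b = 50% with probability 15%.
- *Clustering.* In that same case, if 75% of late cases had already had the event, the visible difference is 0.25 × 6 = 1.5 points and the probability is 7%.
- *Early pembrolizumab excess.* With b = 30% on placebo and 33% on pembrolizumab, and 10% v 5% late, the whole-window proportions are 0.33 + 0.67 × 0.10 = 39.7% and 33.5%. The difference is 6.2 points and z = 2.02, against 1.15 without the early excess.

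**The case against.** **The Tier 2 intervals are descriptive.** Section 9.6.2 says so, and the external data monitoring committee reviews safety regularly. This stands: no formal test or efficacy conclusion changes. What is lost is the visibility of a signal.

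**Grade 3 to 5 and serious AEs are compared separately.** This also stands. A late severe event is masked only by an earlier one of the same class, where b is plausibly low and the loss smaller. Each is still one proportion with no phase split.

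**Immune-mediated events are evaluated separately.** A reader might infer that this evaluation omits shared terms such as diarrhea. The documents do not support that: Table 4 treats diarrhea/colitis and nephritis as immune-related, and the special-interest list is not given. The evaluation may help, but without a stated list, method or period it cannot be relied on.

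**Drug-related tables could separate the causes.** Only weakly. They are Tier 3, without intervals, and Section 10.3.5 says causality should generally be assigned to the whole combination.

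**The whole-window table captures early and late excess together.** Correct, and Section 6.6.1 says immune-related events may occur shortly after the first dose. That is a reason to keep it.

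**A post-chemoradiotherapy comparison uses a post-randomization subset.** Correct. Table 4 requires permanent discontinuation for several events, so early stopping may differ by arm. This limits interpretation of the added table and must be shown with it.

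**Conclusion.** The point holds in a limited form. The only between-arm AE comparison stated is the proportion of participants with the event, undivided by phase. For terms that chemoradiotherapy and pembrolizumab can both cause, a post-chemoradiotherapy excess is diluted by (1 − b). Under the assumed 10% v 5%, z falls from 2.98 to between 2.28 (b = 5%) and 0.79 (b = 50%). These figures rest on equal background, independence and no early pembrolizumab excess. Clustering would worsen the loss; an early excess would raise the whole-window difference.

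Three stronger readings go beyond the documents:

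- *The plan would hide late pembrolizumab toxicity in general.* The loss is small where b is low and nil for events that chemoradiotherapy does not cause. No AE rates are given from which to say where each term falls.
- *Section 9.6.2 prescribes one count over the full collection window.* It names no window. That reading is inferred from Section 8.4.1 and the absence of any split.
- *Pembrolizumab or placebo alone begins at Cycle 6.* Section 6.4.1 places chemoradiotherapy within the Q3W period but does not say it fills it; 50 to 56 days ends well before week 15.

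This is an inexpensive improvement to the safety analysis, not an error that undermines it.

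**What to change.** In Section 9.6.2 and Table 10, name the analysis window and keep the whole-window comparison. Add the same difference with Miettinen-Nurminen 95% CI, for AEs, Grade 3 to 5 AEs and SAEs, in two periods:

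1. onset or grade worsening from first dose to completion of chemoradiotherapy;
2. new onset or grade worsening after completion of chemoradiotherapy, among participants still under AE observation then.

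An event in period 1 must not stop the participant counting in period 2. Define the boundary by each participant's own chemoradiotherapy completion date, not by Cycle 6; splitting at Cycle 6 would put about 7 weeks of pembrolizumab or placebo alone into the chemoradiotherapy period. Report by arm how many stopped pembrolizumab or placebo before period 2 and why. Label period 2 as a descriptive comparison in a post-randomization subset. State the list and method for the immune-mediated events of special interest.

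The cost is SAP or supplemental SAP wording and one further set of tables. Section 10.3.5 already requires each grade change to be recorded, and the imaging schedule in Section 8.2.1.2 already depends on the completion date. No new visits, endpoints or alpha are needed, and no treatment rule changes. While editing, reconcile the Tier 2 threshold for SAEs, which is 2% in the text of 9.6.2 and 5% in Table 10.

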| To compare concurrent chemoradiotherapy plus pembrolizumab with concurrent chemoradiotherapy plus placebo with respect to change from baseline score in symptom experience using the European Organization for Research and Treatment of Cancer Quality of Life Questionnaire (Symptom Score for Cervical Cancer) the EORTC QLQ-CX24 symptom specific scale (11 items) | The European Organization for Research and Treatment of Cancer Quality of Life Questionnaire (Symptom Score for Cervical Cancer) EORTC QLQ-CX24 symptom specific scale |
| To evaluate the safety and tolerability of pembrolizumab in combination with concurrent chemoradiotherapy | Adverse events Study treatment discontinuation due to adverse events |

| Objectives | Endpoints |
|----------------------|-----------|
| Tertiary/Exploratory | |

| Objectives | Endpoints |
|------------|-----------|
| | |

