| Secondary Endpoints | 
 • PFS assessed by BICR • PFS at 2 years per RECIST 1.1 as assessed by Investigator or by histopathologic confirmation of suspected disease progression (in the absence of radiographic disease progression per RECIST 1.1) • PFS at 2 years per RECIST 1.1 as assessed by BICR • OS at 3 years • CR rate at 12 weeks after CCRT per RECIST 1.1 as assessed by Investigator and BICR, respectively, in all randomly assigned participants with measurable disease • ORR per RECIST 1.1 as assessed by Investigator and BICR, respectively, in all randomly assigned participants with measurable disease • PFS per RECIST 1.1 as assessed by Investigator or by histopathologic confirmation of suspected disease progression (in the absence of radiographic disease progression per RECIST 1.1) by PD-L1 status (by CPS) • PFS per RECIST 1.1 as assessed by BICR by PD-L1 status (by CPS) • OS by PD-L1 status (by CPS) • PFS2: The time from randomization to subsequent disease progression after initiation of new anticancer therapy, or death from any cause, whichever occurs first • Patient-reported quality of life by EORTC QLQ-C30 global score and physical function subscale, and EORTC QLQ-CX24 symptom specific subscale • Safety and tolerability of the 2 treatment arms |
| Statistical Methods for Key Efficacy Analyses | 
The primary hypotheses will be evaluated by comparing the treatment groups with respect to PFS and OS using a stratified log-rank test. The hazard ratio will be estimated using a stratified Cox regression model. Progression-free survival at 2 years and OS at 3 years will be estimated using the Kaplan-Meier method.
 |

| | |
|---|---|
| Statistical Methods for Key Safety Analyses | The analysis of safety results will follow a tiered approach. The tiers differ with respect to the analyses that will be performed. There are no events of interest that warrant elevation to Tier 1 events in this study. Tier 2 parameters will be assessed via point estimates with 95% CIs provided for between-group comparisons; only point estimates by treatment group are provided for Tier 3 safety parameters. The 95% CIs for the between-treatment differences in percentages will be provided using the Miettinen and Nurminen method [Miettinen, O. and Nurminen, M. 1985]. |

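### Discontinuation due to AEs is a named secondary safety endpoint, yet Section 9 specifies no between-arm difference or interval for it, nor for any Grade 3-5 AE or any SAE

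*Combined protocol and SAP*

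**What the plan says.** The synopsis (1.1) and Section 3 set a secondary safety objective: "To evaluate the safety and tolerability of pembrolizumab in combination with concurrent chemoradiotherapy". Two endpoints stand against it, AEs and "Study treatment discontinuation due to adverse events".

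Section 9.6.2 sorts safety results into tiers. The study has no Tier 1 events. Tier 2 events get a between-arm difference in proportions with a Miettinen-Nurminen 95% CI, and the entry rule is: "Membership in Tier 2 requires that at least 5% participants in any treatment group exhibit the event". Grade 3-5 AEs and SAEs above their own thresholds also enter Tier 2.

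Seven broad categories are then placed in Tier 3 by name: any AE, any drug-related AE, any SAE, any serious drug-related AE, any Grade 3-5 AE, any drug-related Grade 3-5 AE, and finally "discontinuation due to an AE will be considered Tier 3 endpoints. Only point estimates by treatment group are provided for Tier 3 safety parameters". Table 10 agrees. Its row "Discontinuation due to AE", the rows for the other broad categories and a row for death are marked under descriptive statistics only, with nothing under the 95% CI column. Section 9.1 repeats the rule: "only point estimates by treatment group are provided for Tier 3 safety parameters".

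**The concern.** Adding pembrolizumab to curative-intent chemoradiotherapy is judged by setting added toxicity against gains in PFS and OS. Section 4.2.1.1 itself makes an acceptable risk/benefit profile part of the case for PFS as a primary endpoint. The benefit side will be reported as hazard ratios with 95% CIs. The summary measures of added harm, including the only specific safety endpoint that Section 3 names, will be two percentages with no planned statement of how precisely their difference is known.

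The plan's own reasoning does not explain this. The reason Section 9.6.2 gives for its cut is that events below 5% would cloud the overall safety picture and add little. That is a reason for leaving out rare terms. It does not fit a summary such as any Grade 3-5 AE, and no other reason is given for placing these summaries in Tier 3.

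**Working it through.** The plan states no expected AE rates and no precision target for safety, so there is no figure of its own to reproduce. The check has two parts.

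**1. Rule against endpoint list**

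| Quantity | Status in Section 3 | Tier in 9.6.2 and Table 10 | Between-arm 95% CI planned |
|---|---|---|---|
| Discontinuation due to AE | Named secondary endpoint | Tier 3, by name | No |
| Any Grade 3-5 AE | Under the AE endpoint | Tier 3, by name | No |
| Any SAE | Under the AE endpoint | Tier 3, by name | No |
| A single AE term at 5% or more in one arm | Under the AE endpoint | Tier 2, by incidence | Yes |

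With 490 per arm, 5% is 0.05 × 490 = 24.5. A term seen in 25 participants of one arm therefore gets an interval.

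**2. What the Tier 2 method would give for the affected rows**

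Inputs:
- 490 per arm (Section 9.1), assuming all are treated.
- Illustrative rates from the durvalumab phase 3 trial described in Section 2.2.3: discontinuation for AEs possibly related to study drug, 12.5% versus 9.6%; Grade 3/4 AEs, 51.7% versus 51.0%. Neither definition matches this trial's rows exactly, so they only set a scale.

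Counts are 0.125 × 490 ≈ 61, 0.096 × 490 ≈ 47, 0.517 × 490 ≈ 253 and 0.510 × 490 ≈ 250.

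The unstratified Miettinen-Nurminen limits are the values of δ that solve

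(p1 − p2 − δ)² = 1.96² × [r1(1 − r1)/n1 + r2(1 − r2)/n2] × N/(N − 1),

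where p1 and p2 are the observed proportions, r1 and r2 are their maximum-likelihood estimates under r1 − r2 = δ, and N = n1 + n2 = 980.

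| Case | Counts | Difference (points) | 95% CI |
|---|---|---|---|
| Discontinuation, 12.5% vs 9.6% | 61 vs 47 | 2.9 | -1.1 to 6.8 |
| Grade 3/4 AE, 51.7% vs 51.0% | 253 vs 250 | 0.6 | -5.6 to 6.9 |

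A hand check of the first row with the simple Wald formula: p1 = 61/490 = 0.1245 and p2 = 47/490 = 0.0959, so the difference is 0.0286. The standard error is √[(0.1245 × 0.8755 + 0.0959 × 0.9041)/490] = 0.0200. Then 0.0286 ± 1.96 × 0.0200 gives about -1.1 to 6.8 points, in agreement.

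Because the true discontinuation rates are unknown, the same calculation was run over assumed pairs, chosen only to show interval width:

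| Assumed rates | Counts | Difference (points) | 95% CI |
|---|---|---|---|
| 5% vs 5% | 24 vs 24 | 0.0 | -2.8 to 2.8 |
| 10% vs 10% | 49 vs 49 | 0.0 | -3.8 to 3.8 |
| 15% vs 10% | 74 vs 49 | 5.1 | 1.0 to 9.3 |
| 20% vs 10% | 98 vs 49 | 10.0 | 5.6 to 14.5 |

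The half-width for discontinuation is thus roughly 3 to 4.5 points, and about 6 points for a category near 50%.

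**The case against.** The strongest defence is that nothing promised is withheld. The efficacy and PRO objectives are worded as comparisons, the safety objective as an evaluation, and Sections 9.4.2 and 9.6.2 describe safety assessment as clinical review. The Tier 3 rule is stated consistently in three places, so it is deliberate. This stands: a reader might infer a broken commitment or an internal contradiction, and the documents support neither.

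Several other stronger readings also fail.
- A reader might infer that toxicity is compared without any interval. In fact AE and system organ class terms, Grade 3-5 AEs and SAEs above threshold all get between-arm intervals, and immune-mediated events are evaluated separately.
- A reader might infer that the broad categories earned Tier 2 status and lost it. Section 9.6.2 describes classification by observed proportion for specific terms, system organ classes and predefined limits of change; the broad categories are assigned separately. The fair statement is that the stated reason for the 5% cut does not fit them.
- A reader might extend the point to death. All-cause death is OS, which already has a stratified log-rank test and a hazard ratio with 95% CI.
- A reader might extend it to the drug-related categories. Appendix 3 (10.3.5) generally attributes causality to the whole regimen, and both arms receive cisplatin and radiotherapy, so an interval there would say little about toxicity added by pembrolizumab.
- A reader might infer that no interval will ever be reported. The supplemental SAP is not among the documents and could add one, so the claim is limited to what Section 9 specifies.

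It is also true that per-arm counts let a reader compute the interval, and that no alpha or stopping rule depends on it. That limits the harm. It does not explain why the named endpoint should be left for readers to work out when the plan computes the same interval for lesser terms.

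**Conclusion.** The point holds as a gap in estimation. Section 9 specifies no between-arm difference or interval for discontinuation due to AEs, a named secondary endpoint, or for any Grade 3-5 AE or any SAE. The assignment is made by name, so high incidence would not change it.

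What is missing is a statement of precision of roughly ±3 to ±4.5 points for discontinuation and about ±6 points for a category near 50%. These sizes assume 490 treated per arm, an unstratified interval, and rates that are external or assumed. The external discontinuation rates cover only AEs possibly related to study drug, so they are not a forecast for this trial's endpoint. The conclusion about the plan's wording does not depend on any of these rates. The intervals should not be read as tests; the plan's own caveat says that its safety CIs are descriptive.

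**What to change.** In Section 9.6.2, Table 10 and Section 9.1, report the between-arm difference with the Miettinen-Nurminen 95% CI already specified for Tier 2 for three rows: discontinuation due to AE, any Grade 3-5 AE, and any SAE. Give no p-value, and apply the existing caveat that these intervals are unadjusted and descriptive. Either move the rows to Tier 2 or state an exception within Tier 3; the output is the same. Leave death and the drug-related categories as they are.

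The cost is SAP and table-shell wording and three more intervals from a method already planned. Data collection, sample size and alpha are unaffected.
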